5.3. Handling of Dropouts or Missing Data

With the exception of dates, missing data will not be imputed. The method of imputation for any dates that are imputed is described in the relevant sections.

5.4. Multiplicity adjustment

Multiplicity will not be adjusted.

5.5. Patient Disposition

The number and percentage of patients entered into the study, treated in the study, as well as reasons for discontinuation from study treatment and reasons for discontinuation from study, will be summarized overall as well as by treatment cohort. A listing of patient disposition will also be provided.

Significant protocol violations that potentially compromise the data integrity and patients' safety will be summarized for safety population. These violations will include deviations that can be identified programmatically and those that can only be identified by the clinical research associate during monitoring. Significant protocol violations are described in the Trial Issue Management Plan within the study Trial Master File.

5.6. Patient Characteristics

5.6.1. Demographics

Patient demographics will be summarized for safety population. Patient demographics will include country, age, sex, race, ethnicity, height, weight, and body surface area (BSA).

5.6.2. Baseline Disease Characteristics

Eastern Cooperative Oncology Group (ECOG) performance status (PS), initial pathological diagnosis, basis for initial diagnosis, disease stage, histopathological grade, TNM stage and time since initial diagnosis will be summarized for safety population using descriptive statistics and listed in a data listing.

5.6.3. Historical Illnesses

Historical illnesses are clinically relevant events in the past that ended before the screening visit. Historical illnesses (using Preferred Terms [PT] from the most current version of the Medical Dictionary for Regulatory Activities [MedDRA™]) will be summarized.

5.6.4. Prior Therapies

Prior radiotherapy, surgery, systemic and locoregional therapy will be summarized. Prior radiotherapy will be categorized by reason (neoadjuvant, adjuvant, neoadjuvant plus adjuvant, advanced/metastatic) for the regimen and prior surgery will be categorized by intent (curative, palliative). Prior systemic and locoregional therapy will be categorized by treatment intent (curative, palliative) and setting (neoadjuvant, adjuvant, locally advanced, metastatic). Frequency of each specific therapy will be tabulated within each type of regimen and reason for regimen.

5.6.5. Poststudy Treatment Discontinuation Therapies

Therapies received following study treatment discontinuation will be summarized overall and by type of therapy.

5.7. Concomitant Therapy

Concomitant medications including indication for use (primary study condition, AE or medical history event, prophylaxis) will be summarized and listed.

5.8. Safety Analyses

All safety analyses will be performed on the safety population within each cohort. Safety analyses will also be performed combining patients treated within the dose confirmatory phase with patients treated at the same dose level within the dose finding phase.

5.8.1. Extent of Exposure

Drug exposure, dose intensity, drug adjustments (dose omissions, interruptions, reductions) and dose delays for olaratumab, doxorubicin, ifosfamide and mesna will be summarized for all treated patients.

Drug exposure will include the following summaries:

- Number of cycles received per patient
- Duration on therapy: $(\text{date of last cycle Day 1} - \text{date of first dose} + 21) \div 7$, [weeks]
- Cumulative dose: sum of dose administered at each infusion per patient per compound, [mg]
- Weekly dose intensity: the actual cumulative amount of drug taken divided by the duration of treatment in weeks
 - Olaratumab: cumulative dose / last available weight / duration of therapy, [mg/kg/week]
 - Doxorubicin: cumulative dose / BSA derived using last available weight / duration of therapy, [mg/m²/week]
 - Ifosfamide: cumulative dose / BSA derived using last available weight / duration of therapy, [mg/m²/week]
 - Mesna: cumulative dose / BSA derived using last available weight / duration of therapy, [mg/m²/week]
- Relative dose intensity: the actual amount of drug taken divided by the amount of drug prescribed times 100%, [%]

The summary of dose adjustments and delays will include the reason for adjustment or delays.

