7.2.1. Selection and Timing of Doses

A cycle is defined as an interval of 21 days. In Cycle 2 and beyond, up to 3 days delay of a cycle (that is, Day 1) or Day 8 will be permitted due to holidays, weekends, bad weather, or other unforeseen circumstances and will not count as a protocol deviation. In exceptional cases, longer delays may be allowed in later cycles following consultation with Lilly medical representative.

The actual dose of olaratumab to be administered will be determined by measuring the patient's weight in kilograms on Days 1 and 8 of each cycle. See also Section 7.5 for further details on olaratumab. The actual doses of doxorubicin, ifosfamide and mesna to be administered will be determined by calculating the patient's body surface area at the beginning of each cycle. If the patient's weight does not fluctuate by $\pm 10\%$ from the weight used to calculate prior doses, the olaratumab and doxorubicin, ifosfamide and mesna doses will not need to be recalculated, unless deemed clinically meaningful. A $\pm 5\%$ variance in the calculated total doses will be allowed for ease of dose administration.

Patients will continue treatment for a maximum of 6 cycles, or until there is documented disease progression, unacceptable toxicity, death, or other discontinuation criteria are met (Section 8). Patients who discontinue doxorubicin, ifosfamide and mesna treatment without evidence of disease progression will receive olaratumab as monotherapy until there is evidence of disease progression, death, intolerable toxicity, or other withdrawal criteria are met (Section 8). Patients who undergo surgical tumor resection following study treatment are not eligible to receive olaratumab as monotherapy.

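### SAP 5.8.1 divides cumulative dose by the last available weight (or BSA from it), so the reported mg/kg/week and mg/m²/week are wrong when weight changes

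*SAP*

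**What the plan says.** SAP 5.8.1 defines cumulative dose as the milligrams given, summed over infusions. Weekly dose intensity for olaratumab is "cumulative dose / last available weight / duration of therapy". For doxorubicin, ifosfamide and mesna it is "cumulative dose / BSA derived using last available weight / duration of therapy". Neither definition limits the last weight to the dosing period of the drug concerned.

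Protocol 7.2.1 sets the olaratumab dose by "measuring the patient's weight in kilograms on Days 1 and 8 of each cycle". The chemotherapy and mesna doses are "determined by calculating the patient's body surface area at the beginning of each cycle". The same section says doses need not be recalculated while weight stays within ±10% of the weight used for earlier doses, and it allows ±5% variance in the calculated total dose.

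Table JGDR.2 schedules weight and BSA on Days 1 and 8 of Cycles 1-6 and on Day 1 of monotherapy cycles. Table JGDR.3 schedules weight again at Visit 801.

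**The concern.** The milligrams in the numerator were set on a series of weights, and the formula divides them all by one later weight. If weight falls, the result overstates the delivered dose per kg or per m²; if weight rises, it understates it. Chemotherapy stops after at most 6 cycles, while olaratumab monotherapy can continue until progression. Doxorubicin and ifosfamide can therefore be scaled to a weight taken long after their last dose.

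Weekly dose intensity is reported in the same units as the regimen under study, so a reader will compare it directly with the planned 10 mg/kg/week or 25 mg/m²/week. A weight artefact can look like over- or under-delivery.

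**Working it through.** The plan states no figure for this measure, so there is nothing to reproduce first. The check applies the SAP formula to the planned regimen.

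**Inputs from the documents**
- Olaratumab 15 mg/kg on Days 1 and 8, 21-day cycles, 6 cycles: 12 infusions, on days 0, 7, 21, 28, ..., 105, 112 from first dose.
- Duration (SAP 5.8.1): (105 + 21) / 7 = 18 weeks.
- Planned intensity: 15 × 12 / 18 = 10.0 mg/kg/week. Doxorubicin: 75 × 6 / 18 = 25 mg/m²/week.
- Olaratumab reduction from 15 to 12 mg/kg (Table JGDR.8).

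**Assumptions not in the documents**
- Weight changes linearly from the first to the last infusion, by a fraction x, and the last available weight is the one at day 112.
- BSA is proportional to weight^0.5 (Mosteller) or weight^0.425 (DuBois), with height fixed.

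**1. Olaratumab, dose recalculated at every infusion.** The delivered intensity is 10.0 at any weight change. The infusion days sum to 672, and 672/112 = 6, so relative weights sum to 12 − 6x for a loss of x. The SAP value is 15(12 − 6x) / [18(1 − x)] = 10(1 − x/2)/(1 − x).

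| Loss | SAP value (mg/kg/week) |
|---|---|
| 10% | 10 × 0.95/0.90 = 10.56 |
| 15% | 10 × 0.925/0.85 = 10.88 |
| 20% | 10 × 0.90/0.80 = 11.25 |

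**2. Olaratumab, milligrams held fixed within ±10%.** The SAP value is 10/(1 − x).
- 9.9% loss: 10/0.901 = 11.10. By dosing weight it is 10.00. By actual weight at each infusion, (15/18) × Σ 1/(1 − 0.099 × day/112) = 10.53.
- 9.9% gain: 10/1.099 = 9.10 for a patient with no reduction.

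**3. Olaratumab reduced to 12 mg/kg from Cycle 4.** By dosing weight: (6 × 15 + 6 × 12)/18 = 9.00.
- Milligrams not recalculated for weight, 9.9% loss: 9.00/0.901 = 9.99 by the SAP formula; 9.45 by actual weight.
- Recalculated at every infusion: (162 − 75.94x) / [18(1 − x)] = 9.53 at 10% loss and 10.20 at 20%.

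**4. BSA-based drugs.**
- Same linear model, BSA recalculated each cycle: doxorubicin reads about 2.5% (DuBois) to 2.9% (Mosteller) too high at 10% loss, and 5.4% to 6.4% at 20% (26.34 to 26.59 against 25).
- If weight falls 10% or 20% between dosing and the last weight, as could happen after chemotherapy ends, Mosteller gives 0.9^−0.5 = 1.054 or 0.8^−0.5 = 1.118, an error of about 5% or 12%.
- Doxorubicin cut from 75 to 60 mg/m² from Cycle 4, milligrams not recalculated for weight: (3 × 75 + 3 × 60)/18 = 22.5 by dosing BSA. At 9.9% loss the SAP formula gives 23.5 to 23.7. Reaching 25 would take a 19-22% loss.

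**The case against.** **There is no single true value.** Because doses may be carried forward within ±10%, 10.0 is the answer by dosing weight only. In case 2, milligrams per actual kg really do rise, to 10.53. Against that the SAP value is 11.10/10.53 = 1.054, about 5% too high and similar to the protocol's ±5% dosing variance. This stands as a limit on size. It does not rescue the formula, since 11.10 matches neither convention.

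**Dose reductions are not hidden from the report.** A reader might infer that they are. SAP 5.8.1 summarises omissions, interruptions, reductions and delays with reasons, and relative dose intensity (amount taken over amount prescribed) is not tied to the last weight. SAP 5.8.3 also lists TEAEs leading to reductions. Near-complete masking in the intensity figure needs particular conditions, such as case 3 with milligrams not recalculated. With recalculation and 10% loss the reduced patient still reads 9.53. Against an unreduced patient with the same loss, the ratio is 9.53/10.56 = 0.90, as it should be. One reservation: the SAP does not say whether the prescribed amount is taken before or after a reduction.

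**The choice of regimen does not turn on this figure.** A reader might link it to the primary objective. Protocol 5.1.1, 5.1.2, 7.2.2.1 and 9.4.2 base that choice on the number and type of DLTs and on later safety data. Weekly dose intensity is one of several exposure variables in protocol 10.3.2.

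**A systematic bias is not shown.** It is tempting to say that patients who lose weight are also those with reductions. The documents give no weight data, and weight gain distorts the figure the other way.

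**Conclusion.** The formula is wrong as written and should be corrected, but the consequences are modest. For olaratumab on treatment, the error against dosing weight is about 5.6% at 10% loss with recalculated doses. Within the ±10% band and with milligrams fixed, an unreduced patient reads from 9.1 to 11.1 against 10.0. For BSA-based drugs the error is roughly half as large on treatment at the same loss with recalculated doses, and larger if the last weight is taken well after chemotherapy ends. These sizes rest on assumed linear weight paths and assumed losses; the mismatch of weights does not.

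The effect is confined to one descriptive exposure summary. The DLT rules and sample size are untouched. The documents do not support the stronger readings that reductions are lost from the report, that under-delivery is systematically masked, or that the Phase 2 regimen would be chosen on a distorted figure.

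**What to change.** In SAP 5.8.1, define the numerator of weekly dose intensity per infusion: the sum of (mg given / weight used for that dose) for olaratumab, and the sum of (mg given / BSA used for that dose) for doxorubicin, ifosfamide and mesna. Then divide by duration. Where the dosing weight or BSA is not recorded, use the most recent value on or before that infusion. This also covers monotherapy Day 8, where Table JGDR.2 schedules no weight. Keep cumulative mg as a separate line.

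State the convention in the SAP and in the table footnote. Dividing by dosing weight does not show the real rise in mg per actual kg when doses are carried forward during weight loss. It would also help to say whether the prescribed amount in relative dose intensity is the originally planned dose.

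The cost is a wording change and minor programming. No new visits or measurements are needed, but the sponsor should check whether the weight used for each dose is captured, since the documents do not say so.

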Radiologic imaging and measurement of palpable or visible lesions	X			RECIST 1.1 Scans performed prior to the date of consent may be used, provided they are within 28 days of enrollment. Imaging requirements include CT scan or MRI of the chest, abdomen and pelvis and other areas, as clinically indicated. It is recommended that CT imaging of the abdomen/pelvis be performed with IV contrast, whenever possible. If this is not feasible/advisable secondary to hypersensitivity or other conditions, then gadolinium-enhanced MRI is preferred. For patients with known serious allergic reactions to CT contrast material, a CT of the chest without contrast and contrast-enhanced MRI of the abdomen/pelvis are encouraged.
ECG	X			
Echocardiogram and/or MUGA scan	X			
Hematology		X		See Appendix 3 . To be performed locally for patient management and centrally for analysis purposes.
Coagulation		X		See Appendix 3 . To be performed locally.
Clinical chemistry		X		See Appendix 3 . To be performed locally for patient management and centrally for analysis purposes.
Urinalysis		X		See Appendix 3 . To be performed locally.

Serum pregnancy test			X	Applies only to women of childbearing potential. See Appendix 3 . To be performed locally.
Tumor tissue		X		See Section 9.7.2 .
Sample collection				See Appendix 4 .
Pharmacodynamics				
Pharmacokinetics				
Immunogenicity				
Pharmacogenetics				
Other biomarkers				

Abbreviations: AE = adverse event; C1D1 = Cycle 1 Day 1; CT = computed tomography; CTCAE = Common Terminology Criteria for Adverse Events (NCI 2009); ECG = electrocardiogram; ECOG = Eastern Cooperative Oncology Group (Oken et al. 1982); ICF = informed consent form; IV = intravenous; MRI = magnetic resonance imaging; MUGA = multiple-gated acquisition; RECIST 1.1 = Response Criteria in Solid Tumors Version 1.1 (Eisenhauer et al. 2009).

Table JGDR.2. On-Study Treatment Schedule of Activities

Day within Cycle Procedure	Cycles 1-6 (olaratumab + doxorubicin + ifosfamide; (Cycle = 21 days)						Cycles 7-N Olaratumab Monotherapy ^a (Cycle = 21 days)		Instructions
	1	2	3	4	8	15	1	8	
Physical examination	X				X		X		
 • Perform prior to infusion of study drug(s). • Includes weight and BSA.
Vital signs	X	X	X	X	X	X	X		Vital signs include temperature, blood pressure, pulse rate, respiration rate.
Concomitant medication	X						X		Concomitant medications will be recorded continuously throughout the treatment period.

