Administer mesna	X	X	X	X					See Section 7.1.3 for details of mesna administration.
G-CSF	X								The use of G-CSFs is required. Administer according to ASCO and NCCN guidelines. In general, G-CSF products like filgrastim or pegfilgrastim should be administered approximately 24 hours after the completion of cytotoxic chemotherapy (for example, on Day 5 for patients in full-dose ifosfamide cohorts or Day 4 for patients in reduced-dose ifosfamide cohorts).
Sample collection									For all sample collection, see Appendix 4.
Pharmacodynamics									
Pharmacokinetics									
Immunogenicity									
Pharmacogenetics									
Other biomarkers									

Abbreviations: AE = adverse event; ASCO = American Society of Clinical Oncology; BSA = body surface area; C = cycle; CTCAE = Common Terminology Criteria for Adverse Events (NCI 2009); D = day; ECG = electrocardiogram; ECOG = Eastern Cooperative Oncology Group (Oken et al. 1982); G-CSF = granulocyte-colony stimulating factor; IRR = infusion-related reaction; IV = intravenously; LVEF = left ventricular ejection fraction; min = minutes; MUGA = multiple-gated acquisition; NCCN = National Comprehensive Cancer Network; PD = progressive disease; q = every; RBC = red blood cell; RECIST 1.1 = Response Criteria in Solid Tumors Version 1.1 (Eisenhauer et al. 2009).

^a Olaratumab monotherapy schedule applies to patients who have completed 6 cycles of olaratumab plus doxorubicin and ifosfamide and are continuing treatment with olaratumab monotherapy or have discontinued doxorubicin plus ifosfamide and are continuing with olaratumab monotherapy. Note: if a patient discontinues doxorubicin plus ifosfamide treatment prior to completing 6 cycles and is continuing treatment with olaratumab monotherapy, perform procedures according to the olaratumab monotherapy schedule beginning the next cycle after the patient discontinues doxorubicin/ifosfamide.

Table JGDR.3. Post-Treatment Follow-Up Schedule of Activities

Procedure	Short-Term Follow-Up ^a	Long-Term Follow-Up	Instructions
Visit	801	802-8XX	
Physical examination	X		Including weight and vital signs (temperature, blood pressure, pulse rate, respiration rate)
Concomitant medication	X		
AE collection	X		CTCAE Version 4.0.
ECOG performance status	X		

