Statistical Analysis Plan I5B-MC-JGDR

A Phase 1b Study of Olaratumab, Doxorubicin and Ifosfamide in the Treatment of Patients With Advanced or Metastatic Soft Tissue Sarcoma

NCT03283696

Approval Date: 28-Aug-2017

1. Statistical Analysis Plan I5B-MC-JGDR: A Phase 1b Study of Olaratumab, Doxorubicin and Ifosfamide in the Treatment of Patients with Advanced or Metastatic Soft Tissue Sarcoma

Confidential Information

The information contained in this document is confidential and the information contained within it may not be reproduced or otherwise disseminated without the approval of Eli Lilly and Company or its subsidiaries.

Note to Regulatory Authorities: this document may contain protected personal data and/or commercially confidential information exempt from public disclosure. Eli Lilly and Company requests consultation regarding release/redaction prior to any public release. In the United States, this document is subject to Freedom of Information Act (FOIA) Exemption 4 and may not be reproduced or otherwise disseminated without the written approval of Eli Lilly and Company or its subsidiaries..

Olaratumab (LY3012207) Soft Tissue Sarcoma

Study JGDR is a Phase 1b, multicenter, nonrandomized, open-label study of intravenous olaratumab (15 mg/kg on Days 1 and 8 or 20-mg/kg loading dose on Days 1 and 8 in Cycle 1 followed by 15 mg/kg on Days 1 and 8 of subsequent cycles) combined with doxorubicin (25 mg/m² on Days 1, 2, 3), ifosfamide (2.5 g/m² on Days 1, 2, 3, 4) and mesna (≥60% of ifosfamide dose on Days 1, 2, 3, 4) in 21-day cycles in the treatment of patients with advanced or metastatic soft tissue sarcoma. Patients will receive combination treatment for a maximum of 6 cycles followed by olaratumab as monotherapy until there is evidence of disease progression, death, intolerable toxicity, or other withdrawal criteria are met.

Eli Lilly and Company
Indianapolis, Indiana USA 46285
Protocol I5B-MC-JGDR
Phase 1b

Statistical Analysis Plan electronically signed and approved by Lilly on date provided below.

Approval Date: 28-Aug-2017 GMT

2. Table of Contents

Section	Page
1. Statistical Analysis Plan I5B-MC-JGDR: A Phase 1b Study of Olaratumab, Doxorubicin and Ifosfamide in the Treatment of Patients with Advanced or Metastatic Soft Tissue Sarcoma	1
2. Table of Contents	2
3. Revision History	6
4. Study Objectives	7
4.1. Primary Objective	7
4.2. Secondary Objectives	7
4.3. Exploratory Objectives	7
5. A Priori Statistical Methods	8

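### SAP 5.8.1 divides all four drugs' weekly dose intensity by one duration that names no drug, so taken literally olaratumab monotherapy weeks dilute the chemotherapy figures

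*SAP*

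**What the plan says.** SAP 5.8.1 lists the exposure summaries. Duration is given once, as (Day 1 of last cycle − first dose + 21) / 7 in weeks, with no drug attached. Cycles are counted per patient: "Number of cycles received per patient". Cumulative dose is explicitly drug-specific: "Cumulative dose: sum of dose administered at each infusion per patient per compound". Weekly dose intensity then has a line for each of olaratumab, doxorubicin, ifosfamide and mesna, and each divides by the duration. For doxorubicin the line is "Doxorubicin: cumulative dose / BSA derived using last available weight / duration of therapy". Relative dose intensity is defined separately: "Relative dose intensity: the actual amount of drug taken divided by the amount of drug prescribed times 100".

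The SAP's opening study description gives the treatment sequence: "Patients will receive combination treatment for a maximum of 6 cycles followed by olaratumab as monotherapy". Protocol Table JGDR.2 heads the later columns "Cycles 7-N Olaratumab Monotherapy", with 21-day cycles. Its footnote a covers patients who stop chemotherapy before six cycles: "perform procedures according to the olaratumab monotherapy schedule beginning the next cycle after the patient discontinues doxorubicin/ifosfamide". Protocol 10.3.2 also lists duration of therapy as an exposure variable, without defining it by drug.

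**The concern.** Monotherapy periods are numbered as study cycles, so Day 1 of a patient's last cycle can fall well after the last chemotherapy dose. With one duration for all drugs, the chemotherapy numerators stop growing while the denominators continue. Weekly chemotherapy intensity would then reflect how long the patient stayed on olaratumab alone as well as how the chemotherapy was delivered.

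The primary objective is to characterise safety and find a dosing regimen, and the design has a full and a reduced ifosfamide dose. A reader will use the intensity table to judge how much chemotherapy was given per week. Relative dose intensity cannot replace it, because it compares amount taken with amount prescribed and has no time term. It therefore does not reflect delays, which Protocol 7.4.1 allows.

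The effect may also differ by enrolment order. Study completion (Protocol 5.3) is tied to the end of combination therapy in the Dose Confirmation Phase, so late patients may have less on-study monotherapy than early ones. SAP 5.8 also plans analyses "combining patients treated within the dose confirmatory phase with patients treated at the same dose level within the dose finding phase". This is a qualitative possibility only.

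**Working it through.** The documents state no weekly dose intensity, so there is no planned figure to reproduce.

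**Inputs**
- Cycle length: 21 days (Protocol 7.2.1).
- Doxorubicin: 25 mg/m² × 3 days = 75 mg/m² per cycle (Protocol 5.1).
- Ifosfamide, full dose: 2.5 g/m² × 4 days = 10 g/m² per cycle (Protocol 5.1).
- Ifosfamide, reduced: 2.5 g/m² × 3 days = 7.5 g/m² per cycle (Protocol 5.1.3).
- Mesna: at least 60% of ifosfamide, so at least 6 g/m² per full-dose cycle (Protocol 7.1.3).
- Olaratumab: 15 mg/kg × 2 = 30 mg/kg per cycle (Protocol 5.5.1).
- c = chemotherapy cycles, at most 6.
- m = monotherapy cycles. The documents give no value; those below are assumed.

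**Formula.** With no delays, full doses and constant weight:
- Single duration = [21(c + m − 1) + 21] / 7 = 3(c + m) weeks.
- Per-drug chemotherapy duration = 3c weeks.
- Doxorubicin, single duration = 75c / [3(c + m)]; per drug = 75c / 3c = 25 mg/m²/week.
- Ratio = c / (c + m), the same for ifosfamide and mesna when all chemotherapy stops together.

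**Results for c = 6** (totals: doxorubicin 450 mg/m², ifosfamide 60,000 mg/m², mesna at least 36,000 mg/m²; intensities in mg/m²/week)

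| m (assumed) | Weeks | Doxorubicin | Ifosfamide | Mesna (minimum) | Ratio |
|---|---|---|---|---|---|
| 0 | 18 | 25 | 3333 | 2000 | 1.00 |
| 2 | 24 | 18.75 | 2500 | 1500 | 0.75 |
| 6 | 36 | 12.5 | 1667 | 1000 | 0.50 |
| 12 | 54 | 8.33 | 1111 | 667 | 0.33 |

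Every planned chemotherapy dose was given in all four rows. Olaratumab at 15 mg/kg stays at 30(c + m) / [3(c + m)] = 10 mg/kg/week throughout.

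**Comparison with the reduced regimen.** Planned intensity of reduced ifosfamide is 7500 / 3 = 2500 mg/m²/week. This equals the m = 2 row for a patient who received every full-dose infusion.

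**Early discontinuation.** For c = 3 and m = 3, doxorubicin is 225 / 18 = 12.5 with the single duration and 225 / 9 = 25 per drug.

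**Where the simple ratio does not apply**
- One 14-day delay during six chemotherapy cycles, then m = 6: per drug 450 / 20 = 22.5; single duration 450 / 38 = 11.8 (53%).
- Doxorubicin stopped after Cycle 4, ifosfamide after Cycle 6, then two monotherapy cycles (24 weeks): doxorubicin 300 / 24 = 12.5 against 300 / 12 = 25 (50%); ifosfamide 60,000 / 24 = 2500 against 60,000 / 18 = 3333 (75%). Protocol 7.4.2 allows either drug to be stopped separately.

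**The case against.** The best counter-argument is that this is loose wording. SAP 5.8.1 opens by naming the four drugs, so the whole list can be read drug by drug. The duration appears under three slightly different names. Relative dose intensity also carries no per-compound label, yet it only makes sense per drug, so a missing label does not prove that a common duration was meant. This much stands: a reader might infer that monotherapy weeks are certain to enter the chemotherapy denominators, and the documents do not settle that. What does not follow is that the text is adequate. The one formula given produces the diluted figure when applied literally, and two programmers could produce different tables from it.

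It is also fair to say that chemotherapy delivery is reported elsewhere: cumulative dose per drug, relative dose intensity, and omissions, interruptions, reductions and delays with reasons. These limit the harm but do not correct the weekly intensity. Stopping doxorubicin and ifosfamide at different cycles is an unusual case, since most of the protocol's discontinuation rules end the combination together.

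A reader might try to bound m from the study completion definition and the cohort sequence. The documents do not support a bound. Monotherapy is open-ended until progression or another withdrawal criterion. A timeline built without recruitment gaps gives the shortest time for a path and not a ceiling. Even on that basis, the permitted path through three Dose-Finding cohorts, with looks after 6, 9 and 15 patients in each, gives 9 × 21 + 126 + 30 = 345 days. That is 17 cycle starts, or m = 17 − 6 = 11, and any accrual time adds to it.

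**Conclusion.** The point holds as a defect in a stated formula. SAP 5.8.1 gives one duration and uses it for all four drugs; followed literally, it multiplies on-schedule, full-dose chemotherapy intensity by c/(c+m). The size depends on m, which is an assumption here: 75% of the per-drug value at m = 2, 50% at m = 6 and 33% at m = 12, for c = 6. There is no distortion at m = 0 or if the sponsor already intends a per-drug duration.

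The consequence is confined to one descriptive exposure summary and to patients who receive monotherapy. A reader might infer that regimen selection is compromised. It is not: the DLT rules, relative dose intensity, and the summaries of omissions, reductions and delays do not use this duration. Confidence is high that the text is silent on a per-drug duration, and lower on how the table would be programmed.

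**What to change.** In SAP 5.8.1, define duration separately for each drug as (Day 1 of the last cycle in which that drug was given − first dose of that drug + 21) / 7 weeks, and use it in that drug's weekly dose intensity. Use one name for the quantity throughout.

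Report the number of cycles per drug beside it. A per-drug duration alone would hide early stopping: a patient who stops after two full-dose cycles has doxorubicin 150 / 6 = 25 mg/m²/week, the same as one who completes six.

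The cost is SAP wording and programming. Dosing dates by drug and cycle are already needed for the planned cumulative dose and dose-adjustment summaries, so no new data, visits or clinical rules are involved.
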